#### 10.3.4. TEAE Analyses

The counts and percentages of subjects experiencing a TEAE and TEAEs by PTs and SOCs in the following categories will be presented by study treatment arm:

All AE summaries will be restricted to TEAEs. Each AE summary will be displayed by treatment group for DB phase, DBext phase, and combined. Summaries that are displayed by SOC and PT will be ordered by descending order of incidence of SOC and PT within each system organ class.

Summary tables of the following TEAEs will be presented:

- Overall summary of TEAEs
- Patient incidence of TEAEs and the total number of entries by SOC and PT. This summary will be repeated for subgroups specified in [Section 10.10](#).
- Patient incidence of TEAEs by SOC, PT, and highest severity. At each level of patient summarization, a patient is classified according to the highest severity if the patient reported 1 or more events. AEs with missing severity will be considered severe for this summary.
- Patient incidence of TEAEs by SOC, PT, and closest relationship to IP (Related/Not Related). Related AEs are those with relationships reported as “Definite,” “Probable,” or “Possible,” and unrelated AEs are those with relationships reported as “Unlikely” or “Not Related”. At each level of patient summarization, a patient is classified according to the closest relationship if the patient reported 1 or more events. AEs with a missing relationship will be considered related for this summary.
- Patient incidence of serious TEAEs and the total number of entries by SOC and PT.
- Patient incidence of TEAEs leading to IP withdrawal or study discontinuation by SOC and PT. This is a subset of the AEs where Action Taken with Study Treatment is checked as “Drug Withdrawn” or where “Patient Discontinued from Study” is checked on the eCRF.
- Patient incidence of COVID-19 related TEAEs.

Patient incidence will be summarized as subject counts and percentages unless otherwise specified.

The number of AEs and events per 100 patient years will be summarized by SOC and PT.

- Individual patient years = (the last recorded study visit date – first dose date +1)/365.25  
where: the last recorded study visit date = end of study date recorded on end of study CRF page for that patient
- Total patient years on study = sum of all individual patient years within the Safety Population
- Events per 100 patient years =  $\frac{\text{Number of Event} \times 100}{\text{Total Patient Years on Study}}$

The following listings will be presented by treatment group and patient:

- All AEs
- Serious AEs
- Severe AEs
- Treatment-related AEs
- AEs leading to Study Drug Withdrawal or Study Discontinuation
- AEs leading to Death
- TEAEs related to COVID-19
- Major adverse cardiovascular events (excluding deaths)

The original date and time will be shown on all listings of AEs.

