### 10.3.1. Treatment-emergent Adverse Events

An AE is defined as a treatment emergent adverse event (TEAE) if it meets one or more of the following criteria:

- An AE starting on or after the first study drug dose and within 30 days after the last dose of study drug.

- An AE occurring prior to the first study drug dose that worsens (increase in grade) after the first study drug dose.

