### 10.3.5. Pruritus Adverse Events

Pruritus: Treatment-emergent pruritus, defined as any PT including “Prur” will be summarized separately by the treatment group, SOC, and PT as a subset of all TEAEs. This summary will be repeated for subjects with “new or worsened” pruritus events, as defined as follows:

- Mild, moderate, or severe treatment-emergent pruritus events in patients with no pruritus at baseline, or
- Worsening of the severity of the baseline condition in patients with pruritus at baseline.

Baseline pruritus is defined as the Investigator’s rating of severity as collected on the PBC Disease History eCRF. Patients whose baseline severity is severe will be counted as worsening if an AE of pruritus with severe is recorded.

An analysis of treatment-emergent pruritus event days per patient years on study will be performed. The days at each severity grade, including the total days of event, the total patient years on study, and the event days per patient year on study at each severity grade, including the total, will be summarized.

In order to explore the relationship between pruritus and the IP, the following time-to-event analyses will be performed:

- Time to first onset of treatment-emergent pruritus

The time to the start of the first episode = date of onset of first episode – date of first dose of IP + 1.

Patients who never reported an AE of pruritus will be censored at the date of last contact.

- Time to onset of the first moderate or severe treatment-emergent pruritus

The time to the start of the first moderate or severe pruritus = date of onset of the first moderate or severe pruritus – date of first dose of IP +1.

Patients who never reported a moderate or severe AE of pruritus will be censored at the date of completion or discontinuation.

- Time to onset of the first severe treatment-emergent pruritus

The time to the start of the first severe pruritus = date of onset of the first severe pruritus – date of first dose of IP +1.

Patients who never reported a severe AE of pruritus will be censored at the date of completion or discontinuation.

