### **10.3.6. Fatigue Adverse Events**

Fatigue: Treatment-emergent fatigue is defined as any PT which includes “Fatigue.” New or worsened treatment-emergent fatigue is defined as follows:

- Any mild, moderate, or severe treatment-emergent fatigue events in patients with no fatigue at baseline, or
- Worsening of the severity of the baseline condition in patients with fatigue at baseline.

Baseline fatigue is defined as the Investigator’s rating of severity as collected on the PBC Disease History eCRF. Patients whose baseline severity is severe will be counted as worsening if an AE of fatigue with severe is recorded.

An analysis of treatment-emergent fatigue event days per patient years on study will be performed. The days at each severity grade, including the total days of event, the total patient

years on study, and the event days per patient year on study at each severity grade, including the total, will be summarized.

In order to explore the relationship between fatigue and the IP, the following time-to-event analyses will be performed:

- Time to first onset of treatment-emergent fatigue  
The time to the start of the first episode = date of onset of first episode – date of first dose of IP + 1.  
Patients who never reported an AE of fatigue will be censored at the date of last contact.
- Time to onset of the first moderate or severe treatment-emergent fatigue  
The time to the start of the first moderate or severe fatigue = date of onset of the first moderate or severe fatigue – date of first dose of IP + 1.  
Patients who never reported a moderate or severe AE of fatigue will be censored at the date of last contact.
- Time to onset of the first severe treatment-emergent fatigue  
The time to the start of the first severe fatigue will be calculated by date of onset of the first severe fatigue – date of first dose of IP + 1.  
Patients who never reported a severe AE of fatigue will be censored at the data of last contact.

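### Treatment-emergent event rates are divided by patient-years that run to end of study, so off-drug follow-up beyond 30 days dilutes them, and phase and ongoing-patient denominators are not defined

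*SAP*

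**What the plan says.** **Numerator.** SAP Section 10.3.4 states: "All AE summaries will be restricted to TEAEs". Section 10.3.1 gives two routes to treatment-emergent status. The first is "An AE starting on or after the first study drug dose and within 30 days after the last dose of study drug". The second is "An AE occurring prior to the first study drug dose that worsens (increase in grade) after the first study drug dose", which has no closing date. The opening of Section 10 uses the same window for safety analyses, ending 30 days after treatment is discontinued.

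**Denominator.** Section 10.3.4 computes individual patient-years from first dose to the last recorded study visit, and then defines that visit: "the last recorded study visit date = end of study date recorded on end of study CRF page for that patient". These are summed over the Safety Population into one on-study total. Sections 10.3.5 and 10.3.6 use on-study patient-years again for pruritus and fatigue event days.

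**Phases.** Section 10.3.4 also requires: "Each AE summary will be displayed by treatment group for DB phase, DBext phase, and combined". It gives no patient-year definition for either phase alone.

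**Time-to-event censoring.** For first pruritus: "Patients who never reported an AE of pruritus will be censored at the date of last contact". For moderate or severe pruritus: "Patients who never reported a moderate or severe AE of pruritus will be censored at the date of completion or discontinuation"; severe pruritus has the parallel rule. For fatigue: "Patients who never reported an AE of fatigue will be censored at the date of last contact", and the two higher fatigue grades are also censored at last contact.

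**The concern.** A rate per patient-year needs the time in the denominator to be time in which an event could have entered the numerator. Here the numerator closes to new onsets 30 days after last dose, while the denominator stays open until the patient leaves the study. The extra time can only lower the rate, and it lowers it more in an arm with more off-drug follow-up.

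The SAP expects such follow-up. Section 5 tabulates completion of treatment separately from completion of study and records status after treatment. Appendix A (Baseline and Change from Baseline) covers a subject who stops IP and moves to marketed obeticholic acid (OCA).

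Safety is a primary objective. Because extension time varies between patients, crude percentages do not adjust for follow-up. The rate table is the AE summary that should, and as written it cannot be programmed unambiguously for the phase tables or for patients still on study.

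**Working it through.** The SAP states no event rate, expected count or patient-year total, so there is no figure to reproduce. The check applies its own formula.

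**Inputs from the SAP.** New-onset window to last dose + 30 days (10.3.1). Patient-years from first dose to end of study (10.3.4). Double-blind phase of 48 weeks = 336 days, with treatment then continuing until the database lock for that period, approximately 3 years (Section 3).

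**Assumptions, not in the SAP.** Constant event rate while at risk. A share q of an arm stops at day 168 and remains on study to day S; the rest are treated to day S. S = 336, 756 or 1095; q = 15% or 30%. The 15% echoes the discontinuation figure in Section 3.3, but that figure belongs to the pharmacokinetic sample size and is only illustrative here.

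**1. One patient.** Reported rate / at-risk rate = (168 + 30)/S: 198/336 = 0.59, 198/756 = 0.26, 198/1095 = 0.18.

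**2. One arm.** Factor = [(1 − q)S + 198q]/S.

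| End of study, S | q = 15% | q = 30% | Ratio, 30% vs 15% |
|---|---|---|---|
| Day 336 | 315.3/336 = 0.94 | 294.6/336 = 0.88 | 0.93 |
| Day 756 | 672.3/756 = 0.89 | 588.6/756 = 0.78 | 0.88 |
| Day 1095 | 960.45/1095 = 0.88 | 825.9/1095 = 0.75 | 0.86 |

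The last column is the apparent rate ratio between two arms with equal true rates when 30% of one and 15% of the other stop early. The arm that stops more looks safer.

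**3. A milder pattern.** If 15% stop at Week 12 and leave at Week 48 while the others are treated to Week 108 or 156, each stopper is at risk for 12 + 30/7 = 16.3 weeks and contributes 48. The factor is (0.85 × 108 + 0.15 × 16.3)/(0.85 × 108 + 0.15 × 48) = 94.2/99.0 = 0.95, or 135.0/139.8 = 0.97.

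**4. No off-drug follow-up.** If every end-of-study date is at or before last dose + 30 days, the combined table has no off-drug dilution.

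**5. Phase tables.** For a patient treated throughout, dividing double-blind events by whole-study time would give 336/S: 0.67, 0.44 and 0.31 for S = 504, 756 and 1095. Extension events would give the complement: 0.33, 0.56 and 0.69.

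**6. Ongoing patients.** Appendix A (Last Dose Date) foresees subjects ongoing at the time of analysis and supplies a substitute for last dose date. Section 10.3.4 supplies none for a missing end-of-study date, so their patient-years are undefined.

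**7. Censoring.** Last contact, used for first pruritus and all fatigue endpoints, keeps patients in the risk set after new onsets have stopped counting. The date for moderate or severe pruritus could mean completion of treatment or of study. The censoring rules cover patients who never reported the AE, so a patient whose only pruritus begins after the 30-day window is neither an event nor censored.

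**8. With matched time.** Ending patient-years at last dose + 30 days (or end of study if earlier) and cutting them at the phase boundary makes the factor 1.00 for new-onset events in every arm and phase.

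**The case against.** The strongest reply is that this is a descriptive table in about 50 patients. There is no formal hypothesis (Section 2.2) and, by default, no inferential safety comparison (Section 10). The main AE displays are subject counts and percentages, which this denominator does not touch, and the patient-years are openly labelled as on study. All of that stands and limits the priority.

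The reply also rightly blocks several stronger readings that a reader might infer:

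- *No treatment-emergent event can occur in the extra time.* Not so: the worsening criterion has no 30-day limit, so the cap applies to new onsets only.
- *The plan favours OCA.* The SAP does not say which arm stops earlier, or whether patients who stop stay on study.
- *A single percentage describes the error.* Off-drug follow-up is foreseen but its length is not given. Step 3 shows that a different pattern costs only 3% to 5%.
- *Double-blind rates will be about 31% of their true value.* That needs every patient to be followed for about 3 years, whereas that period is the time until all patients finish and the database is locked. It also needs a programmer to choose whole-study time. The SAP leaves the phase denominator unspecified; it does not order that division.
- *The factors carry over to event days.* Days of an event that began inside the window may run past it, so those rates share the denominator but not necessarily the same dilution.

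The mismatch itself survives: the numerator and denominator close on different dates, and two denominators are missing.

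**Conclusion.** The point holds as a should-fix. Whenever a patient is followed more than 30 days after last dose, the stated formula understates the new-onset event rate, and arms with different amounts of off-drug follow-up are not comparable on it. Under the assumptions shown, the reported rate is 0.94 to 0.75 of the at-risk rate, and two arms with equal true rates would show a ratio of 0.93 to 0.86. The combined-table bias is nil if nobody stays beyond 30 days. The missing phase and ongoing-patient denominators are gaps whatever the follow-up; the phase factor of 0.67 to 0.31 applies only if whole-study time were used. The censoring date is mismatched for first pruritus and all fatigue endpoints, and ambiguous for moderate or severe pruritus.

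**What to change.** - In Section 10.3.4, define individual patient-years as (min[last dose + 30 days, end of study or data cut-off] − first dose + 1)/365.25. Sum them by treatment group and, for the double-blind and extension tables, clip them to the phase, assigning events with the same boundary.
- In Section 10.3.1, put the same 30-day limit on the worsening criterion.
- In Sections 10.3.5 and 10.3.6, use this time base for event days, counting only days inside it. Censor every treatment-emergent pruritus and fatigue time-to-event analysis at the same date, for every patient without a treatment-emergent event.
- If on-study rates are wanted instead, keep the present denominator, count all AEs to end of study in the numerator, and still define the phase and ongoing-patient denominators.

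The cost is SAP wording and one derived variable, before database lock. No new data are needed.

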### 10.3.5. Pruritus Adverse Events

Pruritus: Treatment-emergent pruritus, defined as any PT including “Prur” will be summarized separately by the treatment group, SOC, and PT as a subset of all TEAEs. This summary will be repeated for subjects with “new or worsened” pruritus events, as defined as follows:

- Mild, moderate, or severe treatment-emergent pruritus events in patients with no pruritus at baseline, or
- Worsening of the severity of the baseline condition in patients with pruritus at baseline.

Baseline pruritus is defined as the Investigator’s rating of severity as collected on the PBC Disease History eCRF. Patients whose baseline severity is severe will be counted as worsening if an AE of pruritus with severe is recorded.

An analysis of treatment-emergent pruritus event days per patient years on study will be performed. The days at each severity grade, including the total days of event, the total patient years on study, and the event days per patient year on study at each severity grade, including the total, will be summarized.

In order to explore the relationship between pruritus and the IP, the following time-to-event analyses will be performed:

- Time to first onset of treatment-emergent pruritus

The time to the start of the first episode = date of onset of first episode – date of first dose of IP + 1.

Patients who never reported an AE of pruritus will be censored at the date of last contact.

- Time to onset of the first moderate or severe treatment-emergent pruritus

The time to the start of the first moderate or severe pruritus = date of onset of the first moderate or severe pruritus – date of first dose of IP +1.

Patients who never reported a moderate or severe AE of pruritus will be censored at the date of completion or discontinuation.

- Time to onset of the first severe treatment-emergent pruritus

The time to the start of the first severe pruritus = date of onset of the first severe pruritus – date of first dose of IP +1.

Patients who never reported a severe AE of pruritus will be censored at the date of completion or discontinuation.

The analysis of time to first onset of treatment-emergent pruritus AE, time to onset of the first moderate or severe treatment-emergent pruritus, and onset of the first severe treatment-emergent pruritus will include the number of patients with pruritus (first onset, first moderate or severe, first severe), the number of patients without pruritus (censored), and the minimum and maximum times in days. KM estimates will be calculated by treatment group. The tabulation will include the KM estimate methodology using 25th, 50th (median), and 75th percentiles of the medians and corresponding 2-sided 95% CIs, if the medians can be estimated as well as percentage of censored observations. KM estimates will be plotted as a “survival curve” for each treatment group.

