## **7. PBC DISEASE HISTORY**

PBC disease history will be summarized and presented by treatment group and overall for ITT, Safety, and PK Populations. The number and percentage of subjects in each of the following categories will be presented.

- Age at PBC diagnosis
- Duration of PBC in years at time of informed consent
- Time in years from PBC Diagnosis to first dose of UDCA
- History of PBC related pruritus (Yes/No)
- Severity of most recent pruritus event
- Pruritus ongoing at time of screening (Yes/No)

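### Baseline pruritus is not tied to itch that is ongoing at entry, so the new-or-worsened pruritus summary can leave out some patients who enter without pruritus

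*SAP*

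**What the plan says.** Section 10.3.5 plans a summary of all treatment-emergent pruritus and then repeats it for patients with new or worsened events. Two routes lead into the repeated summary:

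- *New*: "Mild, moderate, or severe treatment-emergent pruritus events in patients with no pruritus at baseline, or"
- *Worsened*: "Worsening of the severity of the baseline condition in patients with pruritus at baseline"

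One exception is added: "Patients whose baseline severity is severe will be counted as worsening if an AE of pruritus with severe is recorded". The baseline that decides between the routes is the Investigator's "rating of severity as collected on the PBC Disease History eCRF". No other condition is attached.

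Section 7 lists what will be tabulated from PBC disease history. Three entries concern itch: "History of PBC related pruritus (Yes/No"), "Severity of most recent pruritus event" and "Pruritus ongoing at time of screening (Yes/No").

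Section 10.3.6 uses parallel wording for fatigue. The sentence beginning "Baseline fatigue is defined as the" points to the Investigator's severity rating on the same form. Section 7 has no fatigue entry.

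**The concern.** The severity of a most recent event and the presence of pruritus at entry are different facts. Section 7 treats them as different by listing ongoing status separately. If the only severity rating available is that of the last episode, Section 10.3.5 gives a patient whose itch has resolved a non-zero baseline grade. The patient then has to pass the *worsened* test, although the ordinary meaning of having no pruritus at baseline would put the patient under *new*.

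This also sits badly with two other conventions in the SAP. Appendix A (Baseline and Change from Baseline) takes the last evaluation before first dose as baseline for qualitative parameters, which means status at entry. Section 10.3.1 makes an event that starts after first dose treatment-emergent. A patient without itch at entry can therefore have a treatment-emergent pruritus event that is classed as neither new nor worsened.

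What is at stake is the accuracy of one safety summary. Safety and tolerability is a primary objective (Section 2.1.1), and pruritus is singled out for its own analyses.

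**Working it through.** The SAP states no figure for this point, so there is none to reproduce. The check applies the Section 10.3.5 rule literally to a patient with a history of pruritus that is not ongoing at screening.

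**Inputs**

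- Baseline grade B: severity of the most recent event (Section 7), used as baseline under Section 10.3.5. Values: mild = 1, moderate = 2, severe = 3; none = 0.
- On-study event grade A: mild = 1, moderate = 2, severe = 3.

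**Rule.** The patient is counted as new or worsened if B = 0, or A > B, or A = B = 3 (the exception for a severe baseline).

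**Result for resolved pruritus, literal reading**

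| Resolved episode | Mild event | Moderate event | Severe event |
|---|---|---|---|
| Mild | not counted | counted | counted |
| Moderate | not counted | not counted | counted |
| Severe | not counted | not counted | counted (exception) |

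Counted: 2 + 1 + 1 = 4 of 9. Not counted: 1 + 2 + 2 = 5 of 9.

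**Same patients with B set to 0 when pruritus is not ongoing.** The first condition is met in every cell, so 9 of 9 are counted. Patients with ongoing pruritus keep their recorded grade and are classified as before. Patients with no history are *new* under either reading.

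**What the cells mean.** They are combinations of grades, not shares of patients. The SAP does not say how many patients have resolved pruritus, or how on-study grades are distributed, so 5 of 9 is not a rate of loss. For scale only: about 50 patients randomized 1:1 (Section 3.3) gives 50 / 2 = 25 per arm, so one misclassified patient moves an arm's percentage by 1 / 25 = 4 percentage points.

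**Reach.** The overall treatment-emergent pruritus summary, the event-days analysis and the three time-to-onset analyses in Section 10.3.5 do not use baseline severity. They are unchanged.

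**The case against.** The strongest reply is that the eCRF is not shown. Section 7 is a list of tabulations, not an inventory of form fields. Section 10.3.6 says the same form holds a fatigue severity rating that Section 7 does not list, which suggests that the list may be incomplete. The form could also hold a current pruritus rating. This stands: the source item is inferred. It does not remove the point, because the SAP names no other pruritus severity item and does not tell the programmer to check ongoing status.

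A second reply is that resolved itch is not naturally a condition present at baseline, so a sensible programmer would apply the ongoing flag. That is a fair reading of the intent, but the explicit definition of baseline does not say it. The text permits both classifications.

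Third, the effect is narrow, and this stands in full. The events remain in every other pruritus analysis. Itch is also followed by the Pruritus VAS and the PBC-40 Itch domain (Sections 14.2 and 14.3). No formal hypothesis is tested (Section 2.2), and safety comparisons are descriptive unless otherwise specified (Section 10).

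Three stronger readings are tempting, and the document does not support them:

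- *New-onset pruritus in general is missed.* It is not. Patients with no history, with a more severe event, or with severe on severe are all counted.
- *The loss can be sized.* If 10% to 30% of 25 patients had resolved moderate or severe pruritus and half of them had a mild or moderate event, 0.10 × 25 × 0.5 = 1.25 to 0.30 × 25 × 0.5 = 3.75 patients would drop out. None of these shares comes from the SAP, so the result is not an estimate.
- *The difference between arms shrinks.* The rule applies to both arms. If the same fraction were missed in each, the difference would shrink but the risk ratio would not change. If resolved history were unevenly distributed, the difference could move either way.

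**Conclusion.** The point holds as a limited defect in a definition. Taken literally, Section 10.3.5 excludes from the new-or-worsened summary a patient with resolved pruritus whose on-study event is no more severe than the earlier episode, severe on severe excepted: 5 of 9 grade combinations. For these patients the misclassification can only remove cases, and it can do so in both arms. The number removed cannot be computed from the SAP.

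The conclusion rests on one assumption: that the severity rating cited in Section 10.3.5 is the most-recent-event item in Section 7. If the form holds a separate rating of current pruritus, the remedy is simply to name that item.

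On fatigue, a reader might infer that no baseline source exists and that a new-or-worsened fatigue table should be dropped. The SAP supports neither step. The form is unseen, and Section 10.3.6 defines the category without explicitly planning a table for it. What remains is a request to identify the item.

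**What to change.** Add one sentence to Section 10.3.5: the recorded severity is the baseline pruritus grade only if the item on pruritus ongoing at screening is Yes; otherwise the baseline grade is none. If the form has a distinct current-severity item, name it instead.

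The flag is already listed in Section 7, so no new data are needed and the programming change is small. There are two modest drawbacks. Recurrences of intermittent itch will be counted as new, which a table footnote should state. The flag also describes screening, at least 14 and not more than 28 days before Day 1 (Section 3), so it does not capture a change in that interval.

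For Section 10.3.6, the sponsor should confirm which eCRF item holds the baseline fatigue rating and cite it. Nothing further is asked for there.

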### Time to Event

The time to an event will be calculated in days as the date of the first occurrence of the event - the date of first IP administration + 1.

The time to a pre-treatment adverse event will be calculated as the date of first IP administration - the date of the first occurrence of the adverse event.

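### First-onset times for pruritus and fatigue are zero or negative when a pre-dose AE becomes treatment-emergent by worsening

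*SAP*

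**What the plan says.** SAP Section 10.3.1 gives two routes to treatment-emergent status. The first is onset on or after first dose, up to 30 days after the last. The second is "An AE occurring prior to the first study drug dose that worsens (increase in grade) after the first study drug dose". By construction, an event on the second route has a pre-dose onset.

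Section 10.3.5 builds the pruritus set from all TEAEs: "Treatment-emergent pruritus, defined as any PT including “Prur” will be summarized separately by the treatment group, SOC, and PT as a subset of all TEAEs". Section 10.3.6 selects fatigue by preferred term in the same way. Second-route events therefore belong to both sets.

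For time to first pruritus, Section 10.3.5 sets "The time to the start of the first episode = date of onset of first episode – date of first dose of IP + 1". Section 10.3.6 repeats that formula under "Time to first onset of treatment-emergent fatigue". The higher-grade endpoints refer to the grade concerned, for example "date of onset of the first severe pruritus – date of first dose of IP +1" for pruritus and "date of onset of the first moderate or severe fatigue – date of first dose of IP + 1" for fatigue. No sentence replaces onset by the date of worsening.

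Censoring for the first-onset endpoints is defined only for patients who never reported the symptom as an AE. Both sections then feed these times into Kaplan-Meier estimates by treatment group and report minimum and maximum times.

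Appendix A (Time to Event) has a general rule, "The time to an event will be calculated in days as the date of the first occurrence of the event" less the first dose date plus 1, and a reversed one: "The time to a pre-treatment adverse event will be calculated as the date of first IP administration - the date of the first occurrence".

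**The concern.** The rule that admits events and the rule that times them do not fit together. A patient with mild itch reported in screening that worsens on treatment counts as having treatment-emergent pruritus. The first-onset formula then returns a time at or before the origin. A negative time is not valid input for a survival estimate, and a zero places the event at the origin instead of when the symptom worsened. Because the patient did report the symptom, the censoring rule does not apply either.

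These curves are meant to explore how pruritus and fatigue relate to the investigational product, so an on-treatment worsening should appear at its own date. If it is lost, the number of events behind the curve will also disagree with the TEAE incidence table, which includes that patient.

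**Working it through.** The plan states no figure to reproduce here. The check applies its date rules to the type of event that Section 10.3.1 admits.

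**Inputs**
- First-onset formula (10.3.5, 10.3.6): onset date - first dose date + 1.
- Screening length (Section 3): 14 to 28 days before Day 1. Taking this as the window in which a pre-dose AE would be recorded is an assumption.
- Arm size: about 50 patients randomized 1:1 (Section 3.3), so about 25.

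**First-onset formula.** For onset k days before first dose, time = -k + 1.

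| Onset before first dose | First-onset time |
|---|---|
| 1 day | 0 |
| 2 days | -1 |
| 10 days | -9 |
| 14 days | -13 |
| 28 days | -27 |

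The date of worsening does not appear in the formula. If the grade rises 42 days after first dose, the on-treatment time is 42 + 1 = 43 in every row.

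**Higher-grade formulas.** Take an AE that is mild 10 days before dosing and severe on Day 40.
- First onset: -10 + 1 = -9.
- First moderate or severe, and first severe, with grade-dated records: Day 40 for both, which is correct.
- The same two endpoints, if one onset date is kept for the whole AE: -9.

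If the AE was already moderate before dosing, the moderate-or-severe endpoint also starts before dosing, even with grade dates.

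**Illustrative effect on the curve.** Assumed: 25 patients; five ordinary events on Days 20, 60, 100, 150 and 250; m further patients whose pre-dose AE worsens on Day 43; everyone else censored on Day 336. With no earlier censoring, the Day 336 Kaplan-Meier incidence equals the simple proportion.

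| m | Dated at worsening: (5 + m)/25 | Dropped as invalid: 5/(25 - m) |
|---|---|---|
| 1 | 6/25 = 24.0% | 5/24 = 20.8% |
| 2 | 7/25 = 28.0% | 5/23 = 21.7% |
| 3 | 8/25 = 32.0% | 5/22 = 22.7% |

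These figures only show how much a few patients matter in an arm of this size. The documents do not give m.

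**The case against.** The best defence is that the gap is narrow. Baseline pruritus and fatigue are taken from the PBC Disease History eCRF (10.3.5, 10.3.6), and Section 7 records pruritus ongoing at screening as disease history. A patient with long-standing symptoms who worsens on treatment would ordinarily have an AE that starts after first dose, and the formula then works. What remains is an AE first reported between screening and Day 1 that later worsens and keeps its onset date. If each grade increase opens a new AE record, even that disappears. Non-positive values would also show up in the reported minimum times. All of this stands and limits the size of the problem. It does not remove it: the SAP states no new-record convention, and its second TEAE criterion presupposes a pre-dose onset.

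Three stronger readings are tempting, but the text does not support them.
- A reader might infer that all six time-to-event analyses fail. The moderate-or-severe and severe formulas refer to the onset of that grade, and the planned summary of days at each severity grade suggests that grade dates exist.
- A reader might infer that Appendix A turns these events into false early times, for example +10 for onset 10 days before dosing. Sections 10.3.5 and 10.3.6 have their own formulas for treatment-emergent events, and nothing sends a TEAE to the pre-treatment rule.
- A reader might infer that pre-dose days inflate the event-day rates. No rule says those days are counted from a pre-dose onset.

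**Conclusion.** The point holds for time to first pruritus and time to first fatigue. For a TEAE that qualifies by worsening and keeps its pre-dose onset date, the stated formula gives zero or a negative time (0 to -27 for onset 1 to 28 days before dosing), and no censoring rule applies. For the moderate-or-severe and severe endpoints it holds only if that grade was already present before dosing or a single onset date serves the whole AE.

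The likely scope is a few AEs arising between screening and Day 1, but the number is unknown. The analyses are descriptive: Section 2.2 sets no formal hypothesis, and no test is attached to these curves. The consequence is therefore a distorted curve, quartile or minimum time, and no primary conclusion changes. It is still worth correcting before database lock, because the rule as written yields an unusable value and the correction is small.

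**What to change.** In Sections 10.3.5 and 10.3.6, add for a TEAE that qualifies by worsening of a pre-dose AE:

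- (a) First onset: the first date on or after first dose when severity exceeds the pre-dose severity.
- (b) First moderate or severe: the first date on or after first dose when severity exceeds the pre-dose severity and is at least moderate.
- (c) First severe: the first date on or after first dose when severity exceeds the pre-dose severity and is severe.

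State also that the Appendix A formula for pre-treatment AEs does not apply to these Kaplan-Meier analyses.

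The wording must differ by endpoint. For an AE that is mild before dosing, moderate on Day 20 and severe on Day 40, the rules give Day 20, Day 20 and Day 40. One common date for all three endpoints would put first severe onset at Day 20, which is wrong. Under each rule the time is at least 1.

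The cost is a few sentences and a little programming from severity-change dates. If only maximum severity is recorded, a few events will need manual dating. If the eCRF already opens a new record at each worsening, one sentence saying so is enough.
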